Appendix 11b: Columbia Suicide Severity Rating Scale (Since Last Visit)

SUICIDAL IDEATION					

Ask questions 1 and 2. If both are negative, proceed to "Suicidal Behavior" section. If the answer to question 2 is "yes," ask questions 3, 4 and 5. If the answer to question 1 and/or 2 is "yes", complete "Intensity of Ideation" section below.
 
1. Wish to be Dead Subject endorses thoughts about a wish to be dead or not alive anymore, or wish to fall asleep and not wake up. Have you wished you were dead or wished you could go to sleep and not wake up?
 
If yes, describe:
		Since Last Visit			

2. Non-Specific Active Suicidal Thoughts General, non-specific thoughts of wanting to end one's life/commit suicide (e.g. "I've thought about killing myself") without thoughts of ways to kill oneself/associated methods, intent, or plan during the assessment period. Have you actually had any thoughts of killing yourself?
 
If yes, describe:
		Yes No  			

3. Active Suicidal Ideation with Any Methods (Not Plan) without Intent to Act Subject endorses thoughts of suicide and has thought of at least one method during the assessment period. This is different than a specific plan with time, place or method details worked out (e.g. thought of method to kill self but not a specific plan). Includes person who would say, "I thought about taking an overdose but I never made a specific plan as to when, where or how I would actually do it.....and I would never go through with it". Have you been thinking about how you might do this?
 
If yes, describe:
		Yes No  			

4. Active Suicidal Ideation with Some Intent to Act, without Specific Plan Active suicidal thoughts of killing oneself and subject reports having some intent to act on such thoughts, as opposed to "I have the thoughts but I definitely will not do anything about them". Have you had these thoughts and had some intention of acting on them?
 
If yes, describe:
		Yes No  			

5. Active Suicidal Ideation with Specific Plan and Intent Thoughts of killing oneself with details of plan fully or partially worked out and subject has some intent to carry it out. Have you started to work out or worked out the details of how to kill yourself? Do you intend to carry out this plan?
 
If yes, describe:
		Yes No  			
INTENSITY OF IDEATION					

The following features should be rated with respect to the most severe type of ideation (i.e., 1-5 from above, with 1 being the least severe and 5 being the most severe).
 
Most Severe Ideation: _____
 
 
 Type # (1-5)	Description of Ideation	Most Severe	
 
 
Frequency How many times have you had these thoughts? (1) Less than once a week (2) Once a week (3) 2-5 times in week (4) Daily or almost daily (5) Many times each day
 
Duration When you have the thoughts, how long do they last? (1) Fleeting - few seconds or minutes (4) 4-8 hours/most of day (2) Less than 1 hour/some of the time (5) More than 8 hours/persistent or continuous (3) 1-4 hours/a lot of time
 
Controllability Could /can you stop thinking about killing yourself or wanting to die if you want to? (1) Easily able to control thoughts (4) Can control thoughts with a lot of difficulty (2) Can control thoughts with little difficulty (5) Unable to control thoughts (3) Can control thoughts with some difficulty (6) Does not attempt to control thoughts
 
Deterrants Are there things - anyone or anything (e.g. family, religion, pain of death) - that stopped you from wanting to die or acting on thoughts of committing suicide? (1) Deterrants definitely stopped you from attempting suicide (4) Deterrants most likely did not stop you (2) Deterrants probably stopped you (5) Deterrants definitely did not stop you (3) Uncertain that deterrants stopped you (6) Does not apply; wish to die only
 
Reasons for Ideation What sort of reasons did you have for thinking about wanting to die or killing yourself? Was it to end the pain or stop the way you were feeling (in other words you couldn't go on living with this pain or how you were feeling) or was it to get attention, revenge or a reaction from others? Or both? (1) Completely to get attention, revenge or a reaction from others. (4) Mostly to end or stop the pain (you couldn't go on living with the pain or how you were feeling). (2) Mostly to get attention, revenge or a reaction from others. (5) Completely to end or stop the pain (you couldn't go on living with the pain or how you were feeling). (3) Equally to get attention, revenge or a reaction from others and to end/stop the pain.
		Type # (1-5)	Description of Ideation	Most Severe	—
Type # (1-5)	Description of Ideation	Most Severe			

Version 7/19/08

10.12. Appendix 12: Arizona sexual experiences scale (ASEX)©

Male:

For each item, please indicate your **OVERALL** level during the **PAST WEEK**, including **TODAY**.

1. How strong is your sex drive?

1 Extremely strong	2 Very strong	3 Somewhat strong	4 Somewhat weak	5 Very weak	6 No sex drive
--------------------------	------------------	-------------------------	-----------------------	----------------	-------------------

2. How easily are you sexually aroused (turned on)?

1 Extremely easily	2 Very easily	3 Somewhat easily	4 Somewhat difficult	5 Very difficult	6 Never aroused
--------------------------	------------------	-------------------------	----------------------------	---------------------	--------------------

3. Can you easily get and keep an erection?

1 Extremely easily	2 Very easily	3 Somewhat easily	4 Somewhat difficult	5 Very difficult	6 Never
--------------------------	------------------	-------------------------	----------------------------	---------------------	------------

4. How easily can you reach an orgasm?

1 Extremely easily	2 Very easily	3 Somewhat easily	4 Somewhat difficult	5 Very difficult	6 Never reach orgasm
--------------------------	------------------	-------------------------	----------------------------	---------------------	-------------------------

5. Are your orgasms satisfying?

1 Extremely satisfying	2 Very satisfying	3 Somewhat satisfying	4 Somewhat unsatisfying	5 Very unsatisfying	6 Can't reach orgasm
------------------------------	-------------------------	-----------------------------	-------------------------------	---------------------------	-------------------------

COMMENTS:

Female:

For each item, please indicate your **OVERALL** level during the **PAST WEEK**, including **TODAY**.

1. How strong is your sex drive?

1 Extremely strong	2 Very strong	3 Somewhat strong	4 Somewhat weak	5 Very weak	6 No sex drive
--------------------------	------------------	-------------------------	-----------------------	----------------	-------------------

2. How easily are you sexually aroused (turned on)?

1 Extremely easily	2 Very easily	3 Somewhat easily	4 Somewhat difficult	5 Very difficult	6 Never aroused
--------------------------	------------------	-------------------------	----------------------------	---------------------	--------------------

3. How easily does your vagina become moist or wet during sex?

1 Extremely easily	2 Very easily	3 Somewhat easily	4 Somewhat difficult	5 Very difficult	6 Never
--------------------------	------------------	-------------------------	----------------------------	---------------------	------------

4. How easily can you reach an orgasm?

1 Extremely easily	2 Very easily	3 Somewhat easily	4 Somewhat difficult	5 Very difficult	6 Never reach orgasm
--------------------------	------------------	-------------------------	----------------------------	---------------------	-------------------------

5. Are your orgasms satisfying?

1 Extremely satisfying	2 Very satisfying	3 Somewhat satisfying	4 Somewhat unsatisfying	5 Very unsatisfying	6 Can't reach orgasm
------------------------------	-------------------------	-----------------------------	-------------------------------	---------------------------	-------------------------

COMMENTS:

©1997, Arizona Board of Regents, University of Arizona. All rights reserved.

This version may be different from the final version in study

10.13. Appendix 13: The Karolinska Sleepiness Scale.

Please, indicate your sleepiness during the 5 minutes before this rating through circling the appropriate description:

- 1=extremely alert
- 2=very alert
- 3=alert
- 4=rather alert
- 5=neither alert nor sleepy
- 6=some signs of sleepiness
- 7=sleepy, but no effort to keep awake
- 8=sleepy, some effort to keep awake
- 9=very sleepy, great effort to keep awake, fighting sleep

(This version may be different from the final version in study)

10.14. Appendix 14: Protocol Amendment History

DOCUMENT HISTORY	
Document	Date
Amendment INT-3	28 August 2019
Amendment INT2, GER-1	04 July 2019
Amendment INT2, GBR-1	21 May 2019
Amendment INT-2	26 February 2019
Amendment INT-1	18-June-2018
Original Protocol	14-March-2018

## 1. INTRODUCTION

JNJ-67953964, previously known as Cerecor (CERC)-501 and LY2456302, is a small molecule, high-affinity, selective kappa opioid receptor (KOR) antagonist. JNJ-67953964 is orally bioavailable and suitable for once-daily (QD) administration.

KORs and their native ligand dynorphin are localized in areas of the brain that effect reward and stress and may play a key role in mood, stress, and addictive disorders. Chronic stress, substance abuse, and acute withdrawal lead to increased dynorphin expression, activating KORs and subsequent downstream signaling pathways to inhibit mesolimbic dopamine surge, contributing to negative affective states. The behavioral pharmacology of KOR antagonism has been tested in animal models of anhedonia, depression, and anxiety and found to have meaningful effects that may translate to therapeutic benefit in humans. KOR antagonists may be effective for the treatment of patients with mood disorders, perhaps by modulating the negative affective state associated with stress response.

Only about 50% of patients with major depressive disorder (MDD) show a meaningful response (>50% improvement to a first line antidepressant treatment), leaving many patients with substantial persistent impairment. Therapeutic strategies such as switching antidepressants and using adjuvant drug treatments can improve response, however almost 40% of patients remain symptomatic and fail to achieve full remission. Recently, Alkermes (ALKS) 5461, a combination of buprenorphine, which is a partial  $\mu$ -opioid receptor agonist and KOR antagonist, and samidorphan, a potent  $\mu$ -opioid receptor antagonist, has been tested in Phase 2 trials in subjects with MDD who have had only a partial response to treatment with a selective serotonin reuptake inhibitor (SSRI) or a serotonin-norepinephrine reuptake inhibitor (SNRI). Adjunctive treatment with ALKS 5461 was associated with greater symptom reduction compared to placebo, suggesting that a KOR antagonist could provide a meaningful clinical benefit for patients being treated for MDD.

A Phase 2a investigator-initiated study (FAST-MAS), evaluated whether JNJ-67953964 engages neural circuitry related to hedonic response to a monetary reward task. Subjects with mood and/or anxiety disorders and anhedonia were randomized to 8 weeks of double-blind treatment with 10 mg JNJ 67953964 (N=43) or placebo (N=44). The primary outcome measure was the functional MRI (fMRI) response to a Monetary Incentive Delay Task conducted at baseline and after 8 weeks of treatment. The activation of brain regions implicated with reward were evaluated with mixed-model analysis of variance (ANOVA) in 68 subjects. Mixed-model analyses revealed a significant Group $\times$ Time interaction in reward gain anticipation ( $p=0.019$ ) (a priori primary outcome) and loss anticipation ( $p<0.001$ ), consistent with relatively greater ventral striatal activation during anticipation of both gain and loss in the JNJ 67953964 group post treatment. The results of this study establish that KOR antagonism has the hypothesized effect on neural function, thereby establishing proof of concept that engaging this target can modulate neuronal circuits relevant to reward and hedonic response.

In the study 67953964MDD2001 the efficacy of JNJ-67953964 compared to placebo is evaluated when administered as adjunctive treatment in subjects with MDD partially responsive to

SSRI/SNRI treatment in terms of reduction of symptoms of depression. Depression in this study is primarily assessed by the change from baseline on the Montgomery Asberg Depression Rating Scale (MADRS) in non-responders during the placebo lead-in period.

The MADRS is a clinician-rated scale designed to measure depression severity and detects changes due to antidepressant treatment. The scale consists of 10 items, each of which is scored from 0 (item not present or normal) to 6 (severe or continuous presence of the symptoms), for a total possible score of 60. Higher scores represent a more severe condition. The MADRS evaluates apparent sadness, reported sadness, inner tension, sleep, appetite, concentration, lassitude, inability to feel (interest level), pessimistic thoughts, and suicidal thoughts. The test exhibits high inter-rater reliability.

The SHAPS is a self-reported 14-item, instrument, developed for the assessment of hedonic capacity. It has excellent internal consistency, with construct validity, and is unidimensional in assessing hedonic capacity among adult patients with MDD. Subjects score whether they experience pleasure in performing a list of activities or experiences. Subjects can rate the answers a “definitely/strongly agree”, “agree”, “disagree” or “strongly disagree”. Answers will be rated according to Franken: “Definitely agree” will be rated 1, “Agree” will be rated 2, “Disagree” will be rated 3, and “Definitely disagree” will be rated 4. So, the score of the scale will range from 14 to 56. The mean score in a population of patients hospitalized for treatment of depression was 34.4.

## 2. OBJECTIVES

The primary objectives of the population pharmacokinetic (PK) and pharmacodynamic (PD) analysis are as follows:

- To characterize the pharmacokinetics of 10 mg qd JNJ-67953964 after oral administration, including
  - an exploratory analysis to determine if any relevant covariate could explain the variability in exposure of JNJ-67953964;
  - derivation of individual exposure parameters for JNJ-67953964 (i.e. area under the plasma concentration-time profile of JNJ-67953964 over 24 hours, AUC0-24h maximum plasma concentration, Cmax, and pre-dose plasma concentrations, C0h). Exposure metrics will be derived from the popPK model on the study days with MADRS and SHAPS assessments;
- To explore the relationship of JNJ-67953964 exposure with efficacy using the change from baseline in Montgomery-Asberg Depression Scale (MADRS) total score and change from baseline in Snaith-Hamilton Pleasure Scale (SHAPS);
- To explore potential relationship between JNJ-67953964 exposure and pre-defined safety parameters. AEs of special interest may include pruritus and gastrointestinal (GI) complaints.

### 3. DATA

The database for population PK analysis and a dataset for the ER analysis will be created by Janssen R&D and/or the external data management provider SGS or Quintiles PK Office based on the clinical databases and according to Janssen R&D specifications. For the three Phase 1 trials, databases are prepared per trial, and merged subsequently with the PK dataset prepared for MDD2001 to establish a pooled PK dataset. The dataset preparation step for the pooled PK dataset should be reviewed according to the internal Janssen Job Aid for Data Flow or Internal Data Preparation. If necessary, minor data management to assemble a suitable NONMEM dataset may be performed. Any modifications to the PK or ER dataset, as well as the merge of the derived individual exposure metrics to the ER dataset will be described in the final report, and the R script used for modification and merging of the data set will be included as an appendix to the final report.

#### 3.1. Description of the Available Data

General information about the studies to be included in the Population PK analysis is summarized [Table 1](#), and for Exposure-Response analysis in [Table 2](#). Further studies may be added as appropriate.

All plasma PK samples with available date and time of both blood collection as well as preceding JNJ-67953964 dose administration will be used for the analysis. Subjects who have not received at least 1 dose of study drug (either JNJ-67953964 or placebo) will not be included in the analysis dataset. PK, MADRS and SHAPS data from subjects with missing dosing information and/or with incomplete dosing may only be included up to the time point of first occurrence of the missing dosing information/incomplete dosing. In case of miss-dosing (e.g. subject took one 5-mg capsule instead of two) the records will be handled as such and not be excluded. Any JNJ-67953964 concentrations before the administration of the first dose of JNJ-67953964 will lead to the exclusion of the subject from the analysis (ie, included in the dataset but commented out).

Baseline is defined as the last observation before the first dose administration of the treatment period (i.e. Treatment baseline) for MADRS, SHAPS and safety parameters. Data from screening and the lead-in period will not be included in the analysis. The primary analysis will be performed on data from the treatment period only.

No records will be deleted from the datasets: records that, for any reason, are excluded from the analysis will be commented out (i.e., including the letter “C” at the beginning of each excluded record or using a designated flag column).

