6. STUDY TREATMENTS

6.1. Study Treatments Administered^a

JNJ-67953964 will be supplied for this study as 5-mg capsules. Placebo will be supplied as matching capsules.

All subjects will take 2 capsules QD. The capsules will be taken daily from Day 2 to Day 78 (at home and when being in the clinic) in fasting condition with some water (fasting for at least 4 hours before dosing; water intake is permitted during that period). Study medication will be taken before breakfast. If the subject has forgotten to take the study medication before breakfast, this should be done before the next following meal, at the latest at dinner of the same day. If the subject remembers later than dinner, the dose of that day should be omitted, and the subject should take his dose before breakfast on the next day.

When Visit 11 is planned up to 3 days later, continue medication until study Visit 11. Spare medication is available in each blister.

The capsules must be swallowed whole and not chewed, divided, dissolved or crushed. After having taken the study medication, subjects should try not to eat or drink for at least 30 minutes. This period should be controlled when the subject is in the clinic. When outside the clinic, violation of this effort (including drug intake in fasting condition) will not be considered a protocol violation.

The first dose will be taken in fasting condition on Day 2 of the double-blind phase when the subject is at home.

The subjects will take the study medication with them at each study visit and will take study medication - from the blisters dispensed at the previous study visit - at the site in fasting

^a This section has been amended by amendment INT-1

condition after completion of predose study assessments and blood collections. Dosing will be witnessed by the study staff.

The dose of the study medication is:

- 10 mg JNJ-67953964: 2 capsules of 5 mg JNJ-67953964
- Placebo: 2 placebo capsules.

Study medication dose may be adjusted to 5 mg QD based on the results of a blinded review of the safety data by the study responsible physician (SRP) or by an unblinded review by the Data Review Committee (DRC) or a physician who is not a member of the study team (See Section 7.1). When a dose reduction has been decided on, this will only apply to new subjects in study and the dose of study medication will be:

- 5 mg JNJ-67953964: 1 capsule of 5 mg JNJ-67953964
- Placebo: 1 placebo capsule.

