### **3.2.3. Missing Date and Time Records**

Concentration records with the following missing information will generally be excluded from the analysis: 1) recorded sampling date and time; 2) dosing information immediately prior to the sample collection time; 3) irresolvable discrepancy between recorded sampling date/time or dosing date/time.

MADRS or SHAPS total score values with the following missing information will generally be excluded from the analysis: 1) recorded assessment date; 2) dosing information on the assessment day; 3) irresolvable discrepancy between recorded MADRS or SHAPS assessment date or dosing date.

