### **3.2.5. Missing Exposure Variable**

If the individual PK parameters cannot be derived due to a lack of consistent or sufficient data, the typical values of PK parameters, taking the individual demographic values into account, will be used to derive the corresponding exposure metrics. If the number of subjects with missing exposure is relatively high (higher than 10%), a sensitivity analysis will be conducted by excluding the subjects with missing exposure.

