**Table 3: Parameters Estimates of Preliminary Updated Population PK Model**

Updated model 6 transit-cmt (data LAF-A,-B,-C)		
Parameter (Units)	Estimate (RSE,%)	IIV (%)
CL/F (L/h)	37.6 (4.81)	28.6
V c /F (L)	399 (5.54)	22.4
Q/F (L/h)	48.6 (6.46)	-
V p /F (L)	847 (6.16)	-
KA (/h)	5.36 (3.25)	23.6
F	1 FIX	26.3
RUV (CV%)	0.161 (10.5)	40.1

IIV = inter-individual variability (%); RSE = residual standard error; CV = coefficient of variation; CL/F = apparent clearance; Vc/F = apparent central volume of distribution; Q/F = apparent intercompartmental clearance; Vp/F = apparent peripheral volumes of distribution; KA = absorption rate constant; RUV = residual unexplained variability.

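### SAP 3.1 can drop observed MADRS and SHAPS scores after the first dosing gap, in both arms, from the exploratory exposure-response analysis, and no sensitivity analysis covers it

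*SAP*

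**What the plan says.** SAP 3.1 sets a subject-level rule for PK, MADRS and SHAPS together: "data from subjects with missing dosing information and/or with incomplete dosing may only be included up to the time point of first occurrence". It does not define incomplete dosing. The next sentence covers a wrong amount: "In case of miss-dosing (e.g. subject took one 5-mg capsule instead of two) the records will be handled as such and not be excluded". The same section adds that "No records will be deleted from the datasets"; excluded records are commented out or flagged.

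SAP 3.2.3 works score by score. MADRS or SHAPS values lacking certain items "will generally be excluded from the analysis: 1) recorded assessment date; 2) dosing information on the assessment day", and likewise where dates conflict beyond resolution. For concentrations, the matching item is "dosing information immediately prior to the sample collection time".

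Protocol 6.1 foresees whole doses being skipped: "If the subject remembers later than dinner, the dose of that day should be omitted". SAP 3.2.2 does not impute missing on-treatment scores. SAP 3.2.5 fills in exposure from typical PK values when individual parameters cannot be derived and, if more than 10% of subjects are affected, "a sensitivity analysis will be conducted by excluding the subjects with missing exposure". That is a different situation from the 3.1 cut-off.

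**The concern.** Under 3.1, one gap in the dosing history can end a subject's contribution to the efficacy model even though later scores were collected. The model in SAP 4.6 estimates a placebo response at each of five post-baseline visits (Treatment Weeks 1, 3, 4, 5 and 6) from these same scores, and neither exclusion rule exempts placebo subjects. Their exposure is zero with or without a dosing record, so the cut-off discards their scores for no gain in exposure accuracy.

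A likelihood-based mixed model tolerates loss that depends only on earlier retained scores. It does not tolerate loss from gaps that track later symptoms or tolerability, and missed doses may well do so. Here the later scores exist, so that assumption need not be made. A first-occurrence cut-off removes more scores at Week 6 than at any earlier visit, and simulations (a) to (c) in SAP 4.7 are read at Week 6. Exploring the relation of PK to efficacy is part of a secondary objective (protocol section 3).

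**Working it through.** The documents state no gap rate and no expected retention, so there is no plan figure to reproduce. The daily gap rate q below is an assumption.

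**One gap.** Post-baseline scores fall on treatment days 7, 21, 28, 35 and 42. With one missing record on treatment day 10, 3.1 keeps 1 of 5 scores and 3.2.3 alone keeps 5 of 5. On day 25 the counts are 2 of 5 and 5 of 5.

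**How many doses can trigger the cut-off.** Treatment runs from Day 22 to Day 64 (SAP Table 1): 64 − 22 = 42 daily doses. Five are taken at clinic visits (Weeks 1, 3, 4, 5, 6) under witness, with date and time entered in the eCRF (protocol 6.1, 6.4). That leaves 42 − 5 = 37 home doses.

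**Week-6 retention.** With independent days, retention = (1 − q)^n. With clustering, it is the beta-binomial probability of no gap, B(a + n, b)/B(a, b), where a = (1 − q)(1/ICC − 1), b = q(1/ICC − 1), and the intraclass correlation (ICC) is assumed to be 0.05 to 0.3.

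| Reading | q = 0.5% | q = 1% | q = 2% |
|---|---|---|---|
| 3.1, 37 home doses, independent | 83% | 69% | 47% |
| 3.1, all 42 doses, independent | 81% | 66% | 43% |
| 3.1, all 42 doses, clustered | 89–96% | 80–93% | 64–86% |
| 3.1, five visit-linked doses | 98% | 95% | 90% |
| 3.2.3 alone | 99.5% | 99% | 98% |

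**In subjects, at q = 1%.** Protocol 9.1 implies 142 × 0.75 × 0.90 ≈ 96 randomised non-responders, and 96 × 0.95 ≈ 91 after dropout. Scores kept at Week 6:
- 37 home doses: 0.689 × 91 ≈ 63
- all 42 doses: 0.656 × 91 ≈ 60
- all 42 doses, clustered: about 73 to 85
- five visit-linked doses: 0.951 × 91 ≈ 87
- 3.2.3 alone: 0.99 × 91 ≈ 90

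**Exposure error if daily dosing is assumed where a record is missing.** Inputs are the SAP Table 3 typical values: CL/F 37.6 L/h, Vc/F 399 L, Q/F 48.6 L/h, Vp/F 847 L, KA 5.36 /h, six transit compartments. Then k10 = 37.6/399 = 0.0942, k12 = 48.6/399 = 0.1218, k21 = 48.6/847 = 0.0574 per hour. The terminal rate is [0.2734 − √(0.2734² − 4 × 0.0942 × 0.0574)]/2 = 0.0215 per hour, a half-life of 32.3 h. Simulating daily dosing to steady state, with the visit-day dose taken, true visit-day AUC0-24h differs from the assumed value as follows.
- Run of 1, 3 or 7 missed days just before the visit: −17%, −33%, −41%. The assumed AUC is then too high by 20%, 49% and 69%.
- Single miss 3, 5 or 7 days before: −6.0%, −2.1%, −0.8%.
- Run of 3 or 7 days whose last missed dose was 7 days before: −1.5%, −1.9%.

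Protocol 2.2.2 reports an AUC accumulation ratio of around 2. On that figure, the drop after a long gap approaches 1 − 1/2 = 50%.

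**The case against.** A reader might infer that 3.1 and 3.2.3 contradict each other and that a missing precedence clause is the defect. The documents do not support that. Both are exclusion rules, both are worded with some discretion, and a score can be required to pass both.

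A reader might also infer that most Week-6 scores would be lost. Among the scenarios above, that happens only at a 2% daily rate with independent days and every home dose or every dose counted. Independence is the least plausible case. Apps prompt and monitor dosing, blisters are returned, and noncompliant subjects can be withdrawn (protocol 6.4, 8.2.3, 7.3).

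The visit-linked reading has textual support. The paragraph in 3.1 opens with the dose preceding each PK sample, and 3.2.3 names the dose before a sample or on the assessment day. On that reading little is lost. It remains a reading, since 3.1 does not say which dose records count, or whether a recorded omission is miss-dosing (kept) or incomplete dosing (cut off).

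Finally, excluding scores where active-arm exposure is uncertain is a defensible conservative choice, and the AUC figures show why. That stands for truly missing active-arm records. It does not justify dropping placebo scores, or active-arm scores where the omission is known and can be coded.

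The SAP also has safeguards: records are flagged, and dataset modifications are reported with the script appended (SAP section 3). These make a rerun possible but do not commit anyone to one.

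**Conclusion.** The concern holds as a minor point. As written, 3.1 lets observed post-gap MADRS and SHAPS scores be dropped in both arms, including placebo scores that carry no exposure uncertainty, with no check on the effect. The size is unknown. The retention figures rest entirely on assumed gap rates and on which doses count, and they run from near-complete to under half at Week 6.

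The scope is narrow. The exposure-response modelling is exploratory, is done only if plots suggest a relationship (SAP 4.6), and is subject to feasibility (protocol 9.4). A reader might carry the point over to the main efficacy result. The documents do not support that, because this SAP governs the population PK and PK/PD analyses and the primary MMRM is specified separately in protocol 9.2.1.

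**What to change.** - Limit the first-occurrence cut-off in SAP 3.1 to PK concentrations.
- Keep observed treatment-period MADRS and SHAPS scores with a valid assessment date in both arms. Set placebo exposure to zero, as SAP 4.8 already does for safety. Derive active-arm exposure from the recorded dosing history, with known omitted doses coded as no dose.
- Align 3.2.3 with this, define incomplete dosing, and state which dose records count as dosing information.
- Run one sensitivity analysis that applies the present cut-off identically in both arms.
- For active-arm scores whose dose records are truly missing, assuming once-daily dosing in the exposure derivation is an option, not a requirement. It overstates exposure if the dose was in fact missed: true visit-day AUC is 17% to 41% lower after 1 to 7 missed days just before the visit by Table 3, and possibly more given the reported accumulation. AUC is also not the whole effect of a gap, since MADRS has a 7-day recall and SAP 4.6 allows for a delayed drug effect.

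The cost is SAP wording and some dataset programming. Excluded records are already flagged, so the sensitivity run is simple.
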